Targeted Physical Examination	X		To assess for potential late emergent study drug related issues, Targeted examination must include at a minimum the following body systems: 
 • Cardiovascular • Gastrointestinal • Pulmonary • Neurological exam for participants with brain metastases
Ophthalmic Evaluation	X		To be performed at Follow Up Visit 1 only, and at any time a participant reports new or worsening visual disturbances (See Section 9.4.3). Not required for Cohort 5 unless clinically indicated.
Echocardiogram or MUGA	X*		*At Follow-up Visit 1 only, not required for Cohort 5 unless clinically indicated.
Adverse Events Assessment	X		Participants will be followed for treatment related toxicities until these toxicities resolve, return to baseline, or are deemed irreversible. All adverse events will be documented for a minimum of 100 days after last dose. (See Appendix 3)
ECG	X		At Follow-up Visit 1 only
Review of Concomitant Medication	X		
Review of Subsequent Cancer Therapies	X	X	Additional subsequent cancer therapy details such as regimen, line of therapy, start date and end date of each regimen, best response to the regimen, and date of progression after additional line of therapy will be collected.

Table 2-7: Follow-Up Period (All treatment cohorts, CA2099N9)

Procedure ^a	Follow-Up, Visits 1 and 2 ^b	Survival Follow-Up Visits ^c	Notes
Laboratory Tests	X		
 Local testing: CBC w/differential and platelet count, Chemistry panel including: AST, ALT, ALP, T.Bili, BUN or serum urea level, creatinine (if abnormal creatinine clearance should be reported), phosphate, Ca, Na, K, Mg, Cl, LDH, glucose, albumin Urinalysis including protein, glucose, blood, leukocyte esterase, specific gravity, pH^d Coagulation including PT/INR and PTT (as clinically indicated) TSH. If TSH is abnormal, see Appendix 5 for instructions on Free T4 and Free T3. 
To be done at FU1. To be repeated at FU2 if study related toxicity persists.

Pregnancy Test (WOCBP only)	X		Serum or urine
Efficacy Assessments			

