Trametinib 1.5 mg QD was the starting dose selected for Cohort 1, 2, and 3 groups. In Part 1, trametinib continuous dosing regimen were investigated initially in Cohort 1, with dose de-escalation and escalation scheme built in for trametinib intermittent dosing regimen, 2 week ON/2 week OFF (Cohort 1 Group). In Part 1A, both trametinib continuous dosing and intermittent dosing was investigated initially in two separate Cohort Groups (Cohort 2 Group and Cohort 3 Group). Specifications regarding trametinib dosing in dose optimization phase can be found in [Section 5.1.1](#).

The totality of the safety data was reviewed, and decision on dose escalation, de-escalation or discontinuation of a particular dosing regimen were made by the study team in conjunction with treating physicians and documented accordingly.

[figure not shown]
- For [REDACTED] | [REDACTED] **(Part 1B) phase**, further evaluations of safety and efficacy will be conducted in Part 1B (triplet regimen; 2L pMMR/MSS mCRC) of the study. Participants who have failed 1 prior line of therapy will be allocated to:
 - Part 1B Cohort 6: One cohort will be initiated in Part 1B to further characterize the safety and preliminary efficacy profile of the triplet regimen. Participants with 2L pMMR/MSS mCRC will be assigned to receive: 6 mg/kg nivolumab (Q4W) plus ipilimumab 1 mg/kg (Q8W) plus trametinib 1.5 mg continuous QD (Cohort 6)
- For [REDACTED] | [REDACTED] **(Part 2) phase**, the efficacy and safety of the investigational triplet regimen versus SOC regimen (regorafenib) in 3L+ (no more than 4 prior lines of therapy) pMMR/mCRC will be evaluated in Part 2, the randomized controlled portion of the trial.
 - Participants will be randomized at 2:1 ratio to receive nivolumab 6 mg/kg Q4W plus ipilimumab 1 mg/kg Q8W plus trametinib 1.5 mg continuous QD (Cohort 4), OR regorafenib in the SOC arm (Cohort 5).

For Part 1B (Cohort 6) and Part 2 (Cohorts 4 and 5), the proportion of participants with RAS mutations will be monitored on an ongoing basis. The IRT system will be set up to notify the Sponsor once the pre-defined number of RAS mutant participants have been enrolled. The target will be approximately 65% mutant, 35% wild type. If accrual diverges significantly from this goal, accrual in a cohort may be paused after discussion between the Sponsor and the investigators. Patients with BRAF V600 mutation are not eligible for the study.

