8 DISCONTINUATION CRITERIA

8.1 Discontinuation from Study Treatment

Participants MUST discontinue investigational product (and non-investigational product at the discretion of the investigator) for any of the following reasons:

- Participant's request to stop study treatment. Participants who request to discontinue study treatment will remain in the study and must continue to be followed for protocol specified follow-up procedures. The only exception to this is when a participant specifically withdraws consent for any further contact with him/her or persons previously authorized by participant to provide this information
- Any clinical adverse event (AE), laboratory abnormality or intercurrent illness which, in the opinion of the investigator, indicates that continued participation in the study is not in the best interest of the participant. Adverse events should be graded and managed according to NCI CTCAE (version 4.0) guidelines.
- Termination of the study by Bristol-Myers Squibb (BMS)
- Loss of ability to freely provide consent through imprisonment or involuntarily incarceration for treatment of either a psychiatric or physical (eg, infectious disease) illness. (Note: Under specific circumstances, and only in countries where local regulations permit, a participant who has been imprisoned may be permitted to continue as a participant. Strict conditions apply and BMS approval is required.)

- Documented radiographic disease progression per RECIST v1.1.
 - Note: For 2L and 3L+ mCRC participants in Cohorts 4 and 6, treatment beyond progression is permitted. See [Section 8.1.5](#).
- Criteria listed in [Section 8.1.1](#) thru [8.1.4](#).
- Requiring treatment as listed in [Section 7.7](#).

Any criteria leading to the discontinuation of nivolumab, ipilimumab, or trametinib as part of the triplet investigative regimen in Parts 1B and 2 will require discontinuation of the entire regimen.

Discontinuation of the study treatment for abnormal liver tests should be considered by the investigator when a participant meets one of the conditions outlined in the protocol ([Section 8.1](#), [Appendix 5](#), and [Appendix 6](#)) or if the investigator believes that it is in best interest of the participant.

Refer to the Schedule of Activities for data to be collected at the time of treatment discontinuation and follow-up and for any further evaluations that can be completed.

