8.1.5 Treatment Beyond Progression

Participants in Cohorts 4 and 6 only, will be permitted to continue treatment beyond initial RECIST 1.1 defined progressive disease (PD), as assessed by the investigator, as long as the following criteria are considered:

- Investigator-assessed clinical benefit
- Tolerance of study drug
- Stable performance status
- Treatment beyond progression will not delay an imminent intervention to prevent serious complications of disease progression (eg, CNS metastases)
- Participant provides written informed consent prior to receiving additional treatment with the investigational study drug regimen. All other elements of the main consent including description of reasonably foreseeable risks or discomforts, or other alternative treatment options will still apply.
- Approval by Medical Monitor/designee.

Radiographic assessment/scan(s) should continue in accordance with the [Section 2](#) Schedule of Activities for the duration of the treatment beyond progression and should be submitted to the central imaging vendor.

If the investigator feels that the participant continues to achieve clinical benefit by continuing treatment, the participant should remain on the trial and continue to receive monitoring according to the Schedule of Activities, presented in [Section 2](#).

For the participants who continue study therapy beyond progression, further progression is defined as an additional 10% increase in tumor burden with a minimum 5 mm absolute increase from time of initial PD. This includes an increase in the sum of diameters of all target lesions and/ or the diameters of new measurable lesions compared to the time of initial PD. It is recommended that study treatment should be discontinued permanently upon documentation of further progression.

New lesions are considered measurable at the time of initial progression if the longest diameter is at least 10 mm (except for pathological lymph nodes which must have a short axis of at least 15 mm). Any new lesion considered non-measurable at the time of initial progression may become measurable and therefore included in the tumor burden if the longest diameter increases to at least 10 mm (except for pathological lymph nodes which must have a short axis of at least 15 mm). In situations where the relative increase in total tumor burden by 10% is solely due to inclusion of new lesions which become measurable, these new lesions must demonstrate an absolute increase of at least 5 mm.

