10.3.2 Safety Analyses

All safety analyses will be performed on the Treated population.

Endpoint	Statistical Analysis Methods

Incidence of DLTs, AEs, SAEs, AEs leading to discontinuation, deaths
 
AEs will be graded according to CTCAE (version 4.0).
	
DLT rate by dose level; Frequency distribution of treated participants with AE using the worst CTC grade.
 
Participants will only be counted (1) once at the preferred term (PT) level, (2) once at the system organ class (SOC) level, and (3) once in the 'Total participant' row at their worst CTC grade, regardless of SOC or PT.
 
Deaths will be summarized using frequency distribution

Laboratory abnormalities
 
Laboratory values will be graded according to CTCAE (version 4.0)
	
Laboratory abnormalities will be summarized.
 
Lab shift table using the worst CTC grade on treatment per participant.

10.3.6 *Outcomes Research Analyses*

10.3.6.3 *Other Analyses*

Not Applicable

10.3.7 *Interim Analyses*

Data were reviewed during the dose escalation/de-escalation evaluation phase (Part 1 and Part 1A) to determine the proposed combination regimens for Part 2 and Part 1B. Comprehensive analyses for Part 1 including safety, [REDACTED], and preliminary efficacy data were conducted to support dose selection for Part 2 (RP2D) as appropriate.

An interim analysis (IA) of Part 2 and Part1B cohorts will be conducted after an overall total of approximately 100 treated participants (including approximately 60 treated participants from Part 2) have a minimum of 4 months of follow-up after the first treatment (corresponding to at least 2 tumor assessments). The objectives of this IA will be a review of the safety data and to provide preliminary efficacy.

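### Part 2 allows treatment beyond progression in the triplet arm only, so adverse-event counting time can differ between arms; crude worst-grade percentages alone cannot separate risk from time observed

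*Combined protocol and SAP*

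**What the plan says.** **Stopping at progression.** Section 8.1 lists "Documented radiographic disease progression per RECIST v1.1" among the reasons for which treatment must stop, with an exception for Cohorts 4 and 6. Section 8.1.5 gives the exception: "Participants in Cohorts 4 and 6 only, will be permitted to continue treatment beyond initial RECIST 1.1 defined progressive disease (PD". It is conditional on clinical benefit, tolerance, stable performance status, further written consent and "Approval by Medical Monitor/designee". Cohort 5 (regorafenib) has no such exception.

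**AE collection.** Table 2-7, which applies to all cohorts, states: "All adverse events will be documented for a minimum of 100 days after last dose". Appendix 3 likewise collects nonserious events through treatment and for at least 100 days after it.

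**Analysis.** Section 10.3.2, in the treated population, gives a "Frequency distribution of treated participants with AE using the worst CTC grade" and, for laboratory values, a "Lab shift table using the worst CTC grade on treatment per participant". It names no person-time rate, cumulative incidence or common observation window.

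**Purpose.** Section 5.1 says that Part 2 will evaluate "the efficacy and safety of the investigational triplet regimen versus SOC regimen (regorafenib) in 3L" and later lines. The safety objective in Table 4-2 is descriptive, with no test or margin.

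**The concern.** A crude percentage with an AE, and a worst grade, can only rise as a participant is watched for longer. Both windows in Section 10.3.2 are tied to dosing: the AE window is treatment plus the 100-day tail, and the laboratory window is treatment itself. Each week of triplet dosing past progression lengthens both, and regorafenib has no counterpart.

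Section 10.3.1 does not have this problem for response and PFS. Best overall response counts assessments only up to first progression or subsequent therapy, and PFS ends at first progression. Post-progression triplet time therefore adds nothing to response or PFS, while its harms are counted in full. At stake is how the randomized safety contrast is read, both at the end and at the Section 10.3.7 interim review: a difference in AE percentages could reflect risk, counting time or both, and the stated tables could not tell these apart.

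**Working it through.** **No figure to reproduce.** The plan states no AE rate, exposure or power for the Part 2 safety contrast. Its one safety probability concerns Parts 1 and 1A (about 82% with 6 participants and 25% incidence) and reproduces: 1 − 0.75⁶ = 0.822.

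**Inputs from the documents.** Regorafenib median PFS of 1.9 months (Table 3.2.2-1), used as a proxy for time on treatment; the 100-day tail in both arms; scans every 8 weeks (Section 9.1.1.2), used as the unit of extra treatment; about 80 versus 40 participants (Section 5.1.3).

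**Assumptions not in the documents.** Exponential time on treatment, equal in both arms apart from continuation past progression. Constant and equal AE hazard h, set so that crude incidence on regorafenib is 20, 40 or 60%. A share f = 10–40% of the triplet arm continues for e = 56–112 days. Deaths cutting the tail short are ignored in both arms.

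**Observation window.** Mean treatment = 1.9 × 30.44 / ln 2 = 83.4 days, so the mean window is 183.4 days. Continuation adds f × e:
- smallest: 0.1 × 56 = 5.6 days, giving 189 days (+3%)
- largest: 0.4 × 112 = 44.8 days, giving 228 days (+24%)

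**Effect on the crude percentage.** With λ = 1/83.4 per day, regorafenib incidence is p₀ = 1 − exp(−100h) × λ/(λ + h). Solving gives h = 0.00124, 0.00292 and 0.00543 per day for p₀ = 20, 40 and 60%. The triplet excess is (1 − p₀) × f × (1 − exp(−h × e)).

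| Regorafenib crude % | f = 10%, e = 56 days | f = 20%, e = 56 days | f = 40%, e = 112 days |
|---|---|---|---|
| 20 | +0.5 | +1.1 | +4.2 |
| 40 | +0.9 | +1.8 | +6.7 |
| 60 | +1.0 | +2.1 | +7.3 |

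Lowest: 0.8 × 0.1 × (1 − exp(−0.00124 × 56)) = 0.08 × 0.067 = 0.005. Highest: 0.4 × 0.4 × (1 − exp(−0.00543 × 112)) = 0.16 × 0.455 = 0.073. Simulating the same model gives +0.6 to +7.3 points, which agrees within simulation error.

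The true hazard ratio here is 1, so an exposure-adjusted rate ratio is 1.00 throughout. A fixed 100-day window gives 1 − exp(−100h) in both arms, so the difference is zero.

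**The other direction.** Give the triplet an extra toxicity stop with an assumed median of 6 or 12 months, with f = 20–40% and e = 56 days. The mean triplet window becomes 171 to 190 days (−7% to +4%), and the crude difference −1.7 to +1.8 points. The sign is no longer determined.

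**Scale.** The 95% half-width of a risk difference, 1.96 × √[p(1 − p)(1/80 + 1/40)], is 15 points at p = 20% and 19 points at p = 40 or 60%.

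**The case against.** **The window is not longer by rule.** A reader might infer that the one-sided permission makes the triplet window longer. It does not: Section 8.1.5 permits continuation in a selected subset, and other rules can shorten triplet exposure. Section 8.1.2 requires discontinuation for Grade 3 drug-related diarrhea or colitis of any duration, whereas Section 7.4.6 interrupts regorafenib for Grade 3 reactions and generally resumes it at a reduced dose. Sections 7.1.4.1, 8.1, 8.1.2 and 8.1.3 also stop the whole triplet when one component stops. The two-year maximum applies to the triplet only, but with a 1.9-month median about 0.02% would still be on treatment by then (exp(−730/83.4)). This objection stands.

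**Bias against the triplet is not established.** That is the next tempting inference. It needs realised exposure to be longer, and the documents do not give it. For the harm of each regimen as given, including permitted continuation, the crude percentage is a proper summary. This also stands, and is why the crude tables should stay.

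**The effect is modest and the analysis descriptive.** True: even +7.3 points lies inside the sampling uncertainty at 80 versus 40. But a systematic component does not average out, and a descriptive contrast is still read as a contrast.

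**Section 10.3 is only a summary.** It announces a separate SAP whose text is not included here, and parts of the section are redacted. Absence from Section 10.3.2 does not prove that exposure-adjusted tables are unplanned. It does mean that the available text does not commit to them.

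**Conclusion.** The point holds as a gap in the stated analysis. AE and on-treatment laboratory observation time can differ between the randomized arms, and Section 10.3.2 states only crude worst-grade summaries, which cannot separate higher risk from longer counting. It does not hold as a claim that the triplet is counted for longer or that its safety is biased unfavourably.

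The size is about +0.5 to +7.3 points if continuation past progression is the only asymmetry, and about −1.7 to +1.8 points once assumed extra toxicity stops are added. Both ranges rest on assumed continuation, extra time, hazards and stop rates. The primary endpoint is unaffected. The change is worth making because it is cheap and holds whichever arm turns out to be observed for longer.

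**What to change.** Keep the crude tables. For Part 2, add by arm in Section 10.3.2 or the SAP:

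- (a) treatment duration and AE observation time;
- (b) exposure-adjusted incidence of AEs, Grade 3–4 AEs and SAEs per 100 person-years of the actual collection window;
- (c) worst-grade AEs within 100 days of first dose, regardless of progression or stopping. The existing collection rule already covers this window in both arms except for death or withdrawal, so show deaths within the window in the same table;
- (d) triplet AEs and worst laboratory grades with onset after first progression, shown separately.

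Read the between-arm contrast from (b) and (c) alongside the crude tables, not from the crude tables alone. A window that closes at progression or 30 days after the last dose would not serve for (c): its length still depends on arm, and it drops late events.

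The rules that determine exposure must also be reconciled. Sections 7.1.4.1, 8.1, 8.1.2 and 8.1.3 end the whole triplet when one component is discontinued, while other paragraphs of Section 8.1 let nivolumab, or nivolumab with trametinib, continue.

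The cost is wording and a few tables from dosing, AE, laboratory and progression dates already collected; no visit, treatment or sample size changes. The rate in (b) assumes a roughly constant hazard, which (c) does not. Table (c) omits later events, which remain in the crude tables.

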12 APPENDICES

APPENDIX 1 ABBREVIATIONS AND TRADEMARKS

Term	Definition
1L	first line
2L	second line
3L	third line
3L+	third line plus
5-FU	5-fluorouracil
AE	adverse event
ALT	alanine aminotransferase
ANC	absolute neutrophil count
ANOVA	analysis of variance
AST	aspartate aminotransferase
AT	aminotransaminases
[REDACTED]	[REDACTED]
BICR	blinded independent central review
[REDACTED]	[REDACTED]
BMS	Bristol-Myers Squibb
BOR	best overall response
BP	blood pressure
BSA	body surface area
BSC	best supportive care
BUN	blood urea nitrogen
C	Celsius
C1	chloride
Ca	calcium
CBC	complete blood count
CEA	carcinoembryonic antigen
CFR	Code of Federal Regulations
cHL	classical Hodgkin's lymphoma
CI	confidence interval
[REDACTED]	[REDACTED]
[REDACTED]	[REDACTED]

Term	Definition
CMS	consensus molecular subtype
CNS	central nervous system
COVID-19	Coronavirus Disease 2019
CR	complete response
CRC	colorectal cancer
CRF	Case Report Form, paper or electronic
CSR	Central Serous Retinopathy
DCR	disease control rate
dl	deciliter
DLT	dose limiting toxicity
dMMR	deficient mismatch repair
DOR	duration of response
ECG	electrocardiogram
ECOG	Eastern Cooperative Oncology Group
eCRF	electronic Case Report Form
EDC	Electronic Data Capture
eg	exempli gratia (for example)
FDA	Food and Drug Administration
FSH	follicle stimulating hormone
g	gram
GCP	Good Clinical Practice
h	Hour
H&N	head and neck
HBsAg	hepatitis B surface antigen
HCG	human chorionic gonadotrophin
HCV	hepatitis C virus
HIV	Human Immunodeficiency Virus
HR	heart rate
HRT	hormone replacement therapy

Term	Definition
ICH	International Conference on Harmonisation
ie	id est (that is)
IEC	Independent Ethics Committee
IHC	immunohistochemistry
IL	interleukin
[REDACTED]	[REDACTED]
IMP	investigational medicinal products
IND	Investigational New Drug Exemption
I-O	Immuno-oncology
IP	investigational product
IRB	Institutional Review Board
irPR	immune-related partial response
irSD	immune-related stable disease
IRT	interactive response technology
IU	International Unit
IV	intravenous
K	potassium
kg	kilogram
L	Liter
LDH	lactate dehydrogenase
LFT	Liver function tests
LLN	lower limit of normal
LPFT	last patient first treatment
LPLV	last patient last visit
LVEF	left ventricular ejection fraction
MAPK	mitogen activated protein kinase
mCRC	metastatic colorectal cancer
MEK	mitogen-activated protein kinase enzymes
mg	milligram
μg	microgram
Mg	magnesium
min	minute

Term	Definition
mL	milliliter
mmHg	millimeters of mercury
MMR	mismatch repair (of DNA)
mOS	median overall survival
MRI	magnetic resonance imagining
MSI	microsatellite instability
MSI-H	microsatellite instability high
MSS	microsatellite stable
MST	medical surveillance team
MTD	maximum tolerated dose
MUGA	multigated acquisition scan
N	number of subjects or observations
Na	sodium
NCCN	national comprehensive cancer network
ng	nanogram
NSCLC	nonsmall cell lung cancer
ORR	objective response rate
OS	overall survival
PD	pharmacodynamic
PD-L1	program cell death ligand 1
PE	physical examination
PFS	progression-free survival
[REDACTED]	[REDACTED]
pMMR	proficient mismatch repair
PPES	Palmar-planta erythrodysesthesia
PO	per os (by mouth route of administration)
[REDACTED]	[REDACTED]
PR	partial response
QD, qd	quaque die, once daily
RCC	renal cell carcinoma
RP2D	Recommended Phase 2 dose

Term	Definition
[REDACTED]	[REDACTED]
RVO	retinal vein occlusion
SAE	serious adverse event
SAP	statistical analysis plan
SD	stable disease
SOP	Standard Operating Procedures
STAT3	Signal transducer and activator of transcription 3
TBD	to be decided
TEAE	treatment-emergent adverse event
Treg	T-regulatory cell
TSH	thyroid stimulating hormone
TTR	time to response
UC	urothelial carcinoma
ULN	upper limit of normal
US	United States
[REDACTED]	[REDACTED]
WBC	white blood cell
WHO	World Health Organization
WOCBP	women of childbearing potential

APPENDIX 2 STUDY GOVERNANCE CONSIDERATIONS

The term 'Participant' is used in the protocol to refer to a person who has consented to participate in the clinical research study. The term 'Subject' used in the eCRF is intended to refer to a person (Participant) who has consented to participate in the clinical research study.

REGULATORY AND ETHICAL CONSIDERATIONS

GOOD CLINICAL PRACTICE

This study will be conducted in accordance with:

- consensus ethical principles derived from international guidelines including the Declaration of Helsinki and Council for International Organizations of Medical Sciences (CIOMS) International Ethical Guidelines Good Clinical Practice (GCP),
- as defined by the International Council on Harmonisation (ICH)
- in accordance with the ethical principles underlying European Union Directive 2001/20/EC
- United States Code of Federal Regulations, Title 21, Part 50 (21CFR50)
- applicable local requirements.

The study will be conducted in compliance with the protocol. The protocol and any amendments and the participant informed consent will receive approval/favorable opinion by Institutional Review Board/Independent Ethics Committee (IRB/IEC), and regulatory authorities according to applicable local regulations prior to initiation of the study.

All potential serious breaches must be reported to Sponsor or designee immediately. A serious breach is a breach of the conditions and principles of GCP in connection with the study or the protocol, which is likely to affect, to a significant degree, the safety or physical or mental integrity of the subjects of the study or the scientific value of the study.

Personnel involved in conducting this study will be qualified by education, training, and experience to perform their respective tasks.

This study will not use the services of study personnel where sanctions have been invoked or where there has been scientific misconduct or fraud (e.g., loss of medical licensure, debarment).

INSTITUTIONAL REVIEW BOARD/INDEPENDENT ETHICS COMMITTEE

Before study initiation, the investigator must have written and dated approval/favorable opinion from the IRB/IEC for the protocol, consent form, participant recruitment materials (e.g., advertisements), and any other written information to be provided to subjects. The investigator or BMS should also provide the IRB/IEC with a copy of the Investigator Brochure or product labeling information to be provided to subjects and any updates.

The investigator, Sponsor or designee should provide the IRB/IEC with reports, updates and other information (e.g., expedited safety reports, amendments, and administrative letters) according to regulatory requirements or institution procedures.

COMPLIANCE WITH THE PROTOCOL AND PROTOCOL REVISIONS

The investigator should not implement any deviation or change to the protocol without prior review and documented approval/favorable opinion of an amendment from the IRB/IEC (and if applicable, also by local health authority) except where necessary to eliminate an immediate hazard(s) to study subjects.

If a deviation or change to a protocol is implemented to eliminate an immediate hazard(s) prior to obtaining relevant approval/favorable opinion(s) the deviation or change will be submitted, as soon as possible to:

- IRB/IEC for
- Regulatory Authority(ies), if applicable by local regulations (per national requirements)

Documentation of approval/favorable opinion signed by the chairperson or designee of the IRB(s)/IEC(s) and if applicable, also by local health authority must be sent to BMS.

If an amendment substantially alters the study design or increases the potential risk to the participant: (1) the consent form must be revised and submitted to the IRB(s)/IEC(s) for review and approval/favorable opinion; (2) the revised form must be used to obtain consent from subjects currently enrolled in the study if they are affected by the amendment; and (3) the new form must be used to obtain consent from new subjects prior to enrollment.

If the revision is done via an administrative letter, investigators must inform their IRB(s)/IEC(s).

FINANCIAL DISCLOSURE

Investigators and sub-Investigators will provide the Sponsor with sufficient, accurate financial information in accordance with local regulations to allow the Sponsor to submit complete and accurate financial certification or disclosure statements to the appropriate health authorities. Investigators are responsible for providing information on financial interests during the course of the study and for 1 year after completion of the study.

INFORMED CONSENT PROCESS

Investigators must ensure that subjects are clearly and fully informed about the purpose, potential risks, and other critical issues regarding clinical studies in which they volunteer to participate.

In situations where consent cannot be given to subjects, their legally acceptable representatives (as per country guidelines) are clearly and fully informed about the purpose, potential risks, and other critical issues regarding clinical studies in which the participant volunteers to participate.

Sponsor or designee will provide the investigator with an appropriate (i.e., Global or Local) sample informed consent form which will include all elements required by ICH, GCP and applicable regulatory requirements. The sample informed consent form will adhere to the ethical principles that have their origin in the Declaration of Helsinki.

Investigators must:

- Provide a copy of the consent form and written information about the study in the language in which the participant is most proficient prior to clinical study participation. The language must be non-technical and easily understood.
- Allow time necessary for participant or participant's legally acceptable representative to inquire about the details of the study.
- Obtain an informed consent signed and personally dated by the participant or the participant's legally acceptable representative and by the person who conducted the informed consent discussion.
- Obtain the IRB/IEC's written approval/favorable opinion of the written informed consent form and any other information to be provided to the subjects, prior to the beginning of the study, and after any revisions are completed for new information.

If informed consent is initially given by a participant's legally acceptable representative or legal guardian, and the participant subsequently becomes capable of making and communicating his or her informed consent during the study, consent must additionally be obtained from the participant.

Revise the informed consent whenever important new information becomes available that is relevant to the participant's consent. The investigator, or a person designated by the investigator, should fully inform the participant or the participant's legally acceptable representative or legal guardian, of all pertinent aspects of the study and of any new information relevant to the participant's willingness to continue participation in the study. This communication should be documented.

The confidentiality of records that could identify subjects must be protected, respecting the privacy and confidentiality rules applicable to regulatory requirements, the subjects' signed ICF and, in the US, the subjects' signed HIPAA Authorization.

The consent form must also include a statement that BMS and regulatory authorities have direct access to participant records.

Subjects unable to give their written consent (e.g., stroke or subjects with or severe dementia) may only be enrolled in the study with the consent of a legally acceptable representative. The participant must also be informed about the nature of the study to the extent compatible with his or her understanding, and should this participant become capable, he or she should personally sign and date the consent form as soon as possible. The explicit wish of a participant who is unable to give his or her written consent, but who is capable of forming an opinion and assessing information to refuse participation in, or to be withdrawn from, the clinical study at any time should be considered by the investigator.

The rights, safety, and well-being of the study subjects are the most important considerations and should prevail over interests of science and society.

BMS COMMITMENT TO DIVERSITY IN CLINICAL TRIALS

The mission of BMS is to transform patients' lives through science by discovering, developing, and delivering innovative medicines that help them prevail over serious diseases.

BMS is committed to doing its part to ensure that patients have a fair and just opportunity to achieve optimal health outcomes.

BMS is working to improve the recruitment of a diverse participant population with the goal that the clinical trial becomes more reflective of the real-world population and the people impacted by the diseases studied.

DATA PROTECTION, DATA PRIVACY, AND DATA SECURITY

BMS collects and processes personal data of study participants, patients, health care providers, and researchers for biopharmaceutical research and development to advance innovative, high-quality medicines that address the medical needs of patients. BMS ensures the privacy, protection, and confidentiality of such personal data to comply with applicable laws. To achieve these goals, BMS has internal policies that indicate measures and controls for processing personal data. BMS adheres to these standards to ensure that collection and processing of personal data are limited and proportionate to the purpose for which BMS collects such personal data. This purpose is clearly and unambiguously notified to the individual at the time of collection of personal data. In the true spirit of science, BMS is dedicated to sharing clinical trial information and data with participants, medical/research communities, the media, policy makers, and the general public. This is done in a manner that safeguards participant privacy and informed consent while respecting the integrity of national regulatory systems. Clinical trial data, health-related research, and pharmacovigilance activities on key-coded health data transferred by BMS across national borders is done in compliance with the relevant data protection laws in the country and GCP requirements.

BMS protects Personal Information with adequate and appropriate security controls as indicated under the data protection laws. To align with the recommended security standards, BMS has adopted internal security standards and policies to protect personal data at every stage of its processing.

To supplement these standards, BMS enters into Clinical Trial Agreements (CTAs) with confidentiality obligations to ensure proper handling and protection of personal data by third parties accessing and handling personal data.

SOURCE DOCUMENTS

The Investigator is responsible for ensuring that the source data are accurate, legible, contemporaneous, original and attributable, whether the data are hand-written on paper or entered electronically. If source data are created (first entered), modified, maintained, archived, retrieved, or transmitted electronically via computerized systems (and/or any other kind of electronic devices) as part of regulated clinical trial activities, such systems must be compliant with all applicable laws and regulations governing use of electronic records and/or electronic signatures. Such systems may include, but are not limited to, electronic medical/health records (EMRs/EHRs),

adverse event tracking/reporting, protocol required assessments, and/or drug accountability records).

When paper records from such systems are used in place of electronic format to perform regulated activities, such paper records should be certified copies. A certified copy consists of a copy of original information that has been verified, as indicated by a dated signature, as an exact copy having all of the same attributes and information as the original.

STUDY TREATMENT RECORDS

Records for study treatments (whether supplied by BMS, its vendors, or the site) must substantiate study treatment integrity and traceability from receipt, preparation, administration, and through destruction or return. Records must be made available for review at the request of BMS/designee or a Health Authority.

If	Then
Supplied by BMS (or its vendors):	
Records or logs must comply with applicable regulations and guidelines and should include:
 
• amount received and placed in storage area• amount currently in storage area• label identification number or batch number• amount dispensed to and returned by each participant, including unique participant identifiers• amount transferred to another area/site for dispensing or storage• nonstudy disposition (e.g., lost, wasted)• amount destroyed at study site, if applicable• amount returned to BMS• retain samples for bioavailability/bioequivalence, if applicable• dates and initials of person responsible for Investigational Product dispensing/accountability, as per the Delegation of Authority Form.
Sourced by site, and not supplied by BMS or its vendors (examples include IP sourced from the sites stock or commercial supply, or a specialty pharmacy)	The investigator or designee accepts responsibility for documenting traceability and study drug integrity in accordance with

If	Then
	requirements applicable under law and the SOPs/standards of the sourcing pharmacy.

BMS or designee will provide forms to facilitate inventory control if the investigational site does not have an established system that meets these requirements.

CASE REPORT FORMS

An investigator is required to prepare and maintain adequate and accurate case histories designed to record all observations and other data pertinent to the investigation on each individual treated or entered as a control in the investigation. Data that are derived from source documents and reported on the CRF must be consistent with the source documents or the discrepancies must be explained. Additional clinical information may be collected and analyzed in an effort to enhance understanding of product safety. CRFs may be requested for AEs and/or laboratory abnormalities that are reported or identified during the course of the study.

For sites using the Sponsor or designee electronic data capture tool, electronic CRFs will be prepared for all data collection fields except for fields specific to SAEs and pregnancy, which will be reported on the electronic SAE form and Pregnancy Surveillance form, respectively. If electronic SAE form is not available, a paper SAE form can be used. Spaces may be left blank only in those circumstances permitted by study-specific CRF completion guidelines provided by Sponsor or designee.

The confidentiality of records that could identify subjects must be protected, respecting the privacy and confidentiality rules in accordance with the applicable regulatory requirement(s).

The investigator will maintain a signature sheet to document signatures and initials of all persons authorized to make entries and/or corrections on CRFs.

